- Questionnaire of Smoking Urges-Brief (QSU-B; Cox et al., 2001): 10-item self-report measure with good reliability and validity for detecting cigarettes craving.
- Medication Adherence Questionnaire (MAQ; Morisky et al., 1986): 4-item self-report measure used to identify potential problems with adherence to a medication regimen including quit smoking aid pharmacotherapies (Toll et al., 2007). Will be given monthly to monitor self-reported compliance with study medication.
- Beck Depression Inventory (BDI, Beck et al., 1961): 21-item self-report measure that evaluates symptoms of depression and suicidal thoughts. Scores are aggregated and categorized as minimal (0-13), mild (14- 19), moderate (20-28) or severe (29-63) depression. Participants who score >20, indicating moderate to severe depression, or who endorse >0 on the suicidal thoughts question (item 9) during screening will be excluded and referred to a clinician for further evaluation and referral if indicated. The BDI will be administered at every study visit to assess ongoing changes to mood.
- Columbia Suicide Severity Rating Scale (C-SSRS; Posner et al., 2003): The C-SSRS is a widely used suicide rating scale that is frequently used in clinical trials that administer varenicline. The C-SSRS will be used at baseline to assess lifetime history of suicidal events, and throughout the study.
- Weekly Update: We will administer a measure designed to assess changes in potential varenicline-mediated side effects over time at every weekly visit. This measure was designed in the context of large-scale trial to assess varenicline for alcohol treatment and was used successfully in a recently completed study to assess varenicline for smoking cessation (NA_00074143).
- Adverse Events Questionnaire: Locally developed measure to query potential side effects and concomitant medications. Specific questions address concerns with new onset of irritable and potentially violent behaviors.

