Study Visits: Participants will attend an initial in-person screening visit, described above, and will return to the clinic on approximately a weekly basis during study weeks 1-12 to receive the intensive pre- post-surgical smoking cessation intervention. Visits during the surgical week will occur prior to the surgery to allow for postsurgical recovery time and we will provide 2 weeks of medication at that visit to allow participants to continue using the medication during their recovery period and provide general flexibility to participants who are unable to complete a visit during their first postsurgical week. Each visit will include collection of a urine sample (that will be tested for urinary cotinine and illicit drug use), a breath CO sample, and self-report questionnaires. None of the data collected during study visits will be shared with the patients' surgical team. Participants will be contacted via phone approximately 3 weeks after study

completion and asked whether they are still abstaining from smoking. Those who endorse continued abstinence will be asked to complete a follow-up visit, during which they will provide a urine sample that will be tested for evidence of cotinine. Participants may be contacted over an additional six month period for follow-up questions pertaining to treatment outcome. Participants will be compensated for attending study visits and completing brief questionnaires and tasks; session payment values will escalate after surgery to encourage continued retention (a standard practice in our treatment protocols) and the total possible study visit compensation will be \$650.

- c. Blinding, including justification for blinding or not blinding the trial, if applicable.

Given that this is an open-label pilot study, all participants will receive the same intensive pre to post-surgical smoking cessation intervention in order to collect the data necessary to illustrate the feasibility of incorporating such an intensive intervention into the hospital setting. This pilot data will be used to support the need for future funding to complete larger randomized controlled trials, and/or multi-site trials. Given that no comparison condition is being included in the current pilot study, the issue of blinding is not applicable at this time.

- d. Justification of why participants will not receive routine care or will have current therapy stopped.

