There is no standard and/or routine access to smoking cessation in elective surgical patients. This study will not disrupt any ongoing routine care associated with the participant's surgery.

- e. Justification for inclusion of a placebo or non-treatment group.

N/A

- f. Definition of treatment failure or participant removal criteria.

Participants failing to continue to meet any of the inclusion/exclusion criteria will be removed from the study and an appropriate clinical referral provided. For example, subjects developing a psychiatric disorder or symptoms requiring treatment (e.g., mania, suicidality, and psychosis), major medical illnesses or serious injuries, which would preclude further participation, will be withdrawn. Subjects who consistently fail to show up for the first treatment session may also be withdrawn.

- g. Description of what happens to participants receiving therapy when study ends or if a participant's participation in the study ends prematurely.

Participants will be debriefed after completing the 1-month follow-up, 6-month follow-up, or premature removal. They will be fully informed about all treatment options for smoking cessation and provided with additional referrals as needed. Any participant who is discharged or voluntarily leaves the study will be provided referrals for obtaining assistance with smoking cessation. The participants will continue meeting with their surgical team, consistent with routine practice for post-surgical patient care and independent of the study.

6. Inclusion/Exclusion Criteria

Inclusion Criteria: We will recruit cigarette smokers who have scheduled an elective surgery to participate in the study. Inclusion criteria will include having a surgery scheduled 5-10 weeks in advance, reporting regular cigarette smoking (smoking 3 times a week or more) and providing a cotinine-positive urine sample.

Exclusion Criteria: Exclusion criteria will include being contraindicated for varenicline use, using products other than cigarettes as a primary nicotine product (including e-cigarettes), providing an illicit drug-positive urinalysis test without evidence of concurrent prescription (e.g., for narcotic pain medications, for example), being pregnant or breastfeeding, or a score >20 on the Beck Depression Inventory-II or a score ≥ 0 on the suicide question of the BDI, past year suicidal ideations or behavior on the C-SSRS, being

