Hospitalization for Non-study Related Injury or Illness: It is likely and expected in this study that some participants will be rehospitalized while still enrolled in the study. We anticipate these hospitalizations will be related to their surgery and will be generally unlikely they will be related to study participation. Nevertheless, in the event of a confirmed hospitalization, study and medical staff will evaluate the event and determine whether it meets criteria for immediate reporting. Events that meet these criteria will be promptly reported to the IRB and NIH in accordance with reporting guidelines of severe adverse events (SAE). The medical monitor of the study will determine whether it is safe for the participant to remain on the study medication or resume its use based upon the specific adverse event.

Pregnancy: There is risk that female participants may become pregnant while enrolled in the study and taking varenicline. Varenicline has been assigned to pregnancy category C drug, indicating there are no adequate and well-controlled studies in humans to assess the safety of varenicline in pregnant women, and therefore is contraindicated for women who are pregnant or breastfeeding. Female participants who plan to become pregnant or who refuse to use adequate methods of birth control during the study will be excluded. Female participants will be tested for pregnancy monthly and if found to be pregnant will be discontinued from the study and varenicline will be stopped immediately.

Questionnaires and Decision-Making Tasks: Minimal risks associated with completing the questionnaires and decision-making tasks are subject fatigue and the possibility of minor psychological distress associated with answering sensitive questions regarding psychological functioning. Participants will be informed that they may choose not to answer any questionnaires that cause discomfort.

Violation of Confidentiality: The risk of violation of confidentiality exists because human subjects are giving personal information.

b. Steps taken to minimize the risks.

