In order to maintain minimal risk we have established exclusion criteria to rule out individuals who might be at more than minimal risk for participating. This includes individuals having a serious and/or untreated medical and/or psychiatric illness. All personnel involved in study procedures will be fully trained in the protocol. Regarding any discomfort that may result from completing study questionnaires or tasks, participants will be informed that they are free to refrain from answering any questions that make them uncomfortable or that they perceive as being particularly personal or sensitive. No participant will be considered ineligible due to declining to answer certain items or specific questionnaires. If information gathered during the study indicates that an individual is in need of emergent psychiatric care (e.g., expressed suicidality), the investigators will place the need for treatment above research considerations. In such cases, the participant will be referred for psychiatric care at Johns Hopkins or in their home community as appropriate.

Specific Protection Against Risks:

Varenicline Administration: To minimize risks associated with varenicline administration, all participants who are deemed high-risk for experiencing varenicline-associated problems will be excluded from study participation. Participants will be informed of the risk and symptoms of an allergic reaction and will be instructed to stop taking varenicline and immediately contact medical staff if they experience any swelling or tingling in the mouth, develop a rash, or observe swelling, redness and/or peeling of the skin. Participants who meet eligibility criteria will be informed of potential varenicline-associated side effects prior to signing the informed consent. Participants will also be able to discuss any potential side effects with a medical professional or qualified study team member prior to providing informed consent to participate. Participants will be informed of the risk of nausea that is associated with varenicline administration and provided methods for alleviating or avoiding nausea (e.g., dose titration as scheduled, consuming divided doses of the medication and consuming varenicline with water and/or food).

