Protection Against the Emergence of Neuropsychiatric Symptoms: The most worrisome potential side-effects of varenicline is the occurrence of rare neuropsychiatric symptoms (suicidal thoughts). Monitoring for such potential side effects will take place via multiple mechanisms. First, participants will be screened with specific questionnaires to history of suicidal thoughts and/or behaviors. Participants with severe prior or current psychiatric symptoms such as psychosis, suicidal behaviors, will be excluded from the study. Second, eligible participants will be informed of the risks for neuropsychiatric side effects and will be instructed to inform a study staff member immediately following any observed change in mood or worrisome thoughts, and will be assessed as clinically indicated. Third, trained staff members will meet with participants on a weekly basis to assess for adverse events using open-ended questions, as well as any emergency room visits and/or hospitalizations that may have occurred. Medical staff will be consulted if the participant endorses any behaviors or thought patterns that signify threats to patient safety or the safety of others, or any adverse event requiring medical attention including vital signs that are out of the norm. Adverse events will be reported to the IRB and the funding agency in accordance with reporting guidelines, and will be recorded as secondary outcome measures. Participants will complete a weekly assessment and the BDI at each study visit. Any endorsement of suicidal thoughts (at any level) on the BDI will prompt administration of the more comprehensive C-SSRS measure to fully characterize suicidal ideation. Any changes in weekly updates, regarding agitation, sadness, or hostility will also prompt assessment by a trained and qualified study investigator. A psychiatrist is always available to assist study staff in the evaluation and management of individual cases. In addition, the Emergency Department and Community Psychiatry department are located on the same campus as the BPRU smoking cessation clinic and are available to provide additional care to participants as needed. Following endorsement of any past 30 day suicidal ideations and/or behaviors, or if determined otherwise necessary by a trained member of the study staff, the individual will be escorted by a staff member to the Emergency Room (located across the street from the BPRU) for further evaluation and/or treatment. Participants will be reminded that they can stop

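### Section 6 excludes a BDI suicide-item score of 0 or above, which every answer meets, where above 0 is meant; a lesser gap is that the Section 9b right to decline has no exception for the suicidality screens

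*Combined protocol and SAP*

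**What the plan says.** **The threshold.** The exclusion list in Section 6 (Inclusion/Exclusion Criteria) contains "a score ≥ 0 on the suicide question of the BDI, past year suicidal ideations or behavior on the C-SSRS". The BDI entry in Section 5a (Screening and Study-related Measures) words the same exclusion differently: those "who endorse >0 on the suicidal thoughts question (item 9) during screening will be excluded". For participants already on study, Section 9b (Protection Against the Emergence of Neuropsychiatric Symptoms) has a separate rule: "Any endorsement of suicidal thoughts (at any level) on the BDI will prompt administration of the more comprehensive C-SSRS measure".

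**The right to decline.** The opening paragraph of Section 9b, in the context of discomfort from questionnaires and tasks, states: "No participant will be considered ineligible due to declining to answer certain items or specific questionnaires". Section 9a (Questionnaires and Decision-Making Tasks) and a later paragraph of Section 9b each add: "Participants will be informed that they may choose not to answer any questionnaires that cause discomfort". None of these three statements makes an exception for BDI item 9 or the C-SSRS at screening.

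**The concern.** The first issue is a decision threshold in the formal eligibility list that cannot be applied as printed. A lower bound of 0 on an item whose lowest score is 0 separates nobody from anybody. For the applicant who scores 0, who is the one the trial wants, Sections 5a and 6 give opposite answers. Anyone auditing enrolment against Section 6 alone would find that every participant who answered the item met an exclusion.

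The second issue concerns what happens before varenicline is first dispensed. Section 9b treats suicidal thoughts as the most serious possible side effect of the drug, and the first protection it lists is screening by questionnaire for a history of suicidal thoughts or behaviour. The instruments that do this are BDI item 9 and the C-SSRS, and each carries an exclusion in Section 6. If both can be left blank with no effect on eligibility, neither exclusion can operate for that applicant. The repeat BDI and weekly staff contact come only after enrolment.

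**Working it through.** No sample size, power or error rate is involved. The check compares rules.

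**Step 1. Range of the item.** The BDI entry in Section 5a gives 21 items and a total running from 0 to 63. If all items have the same range, the maximum per item is 63 / 21 = 3 and the minimum is 0, so item 9 takes the values 0, 1, 2 or 3.

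**Step 2. Apply both rules to every value.**

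| Item 9 score | Section 6 (≥ 0) | Section 5a (> 0) |
|---|---|---|
| 0 | excluded | eligible |
| 1 | excluded | excluded |
| 2 | excluded | excluded |
| 3 | excluded | excluded |
| Total excluded | 4 of 4 | 3 of 4 |

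The rules differ only at 0. The result for 0 does not depend on the assumed maximum of 3, because any score that cannot be negative meets ≥ 0.

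**Step 3. Which rule is intended.** Section 5a excludes scores above 0 and ties this to screening. The on-study rule in Section 9b is triggered by endorsement at any level, which is again any score above 0. Two places agree, and the third cannot be run, so Section 6 holds the error.

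**Step 4. Is the symbol an artefact of text extraction?** This cannot be fully ruled out. However, the same sentence of Section 6 prints > 20 for the BDI total with a different sign, and the ≥ sign reads sensibly in the description of the cotinine dipstick in Section 5a. The symbol is most likely in the source.

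**Step 5. What a blank suicidality screen leaves in force.** If item 9 and the C-SSRS are both blank, the two exclusions that depend on them cannot be met. If only one is blank, the other still applies. The remaining safeguards are:

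- BDI total above 20 (Sections 5a and 6). If only item 9 is skipped, the other 20 items still count, with a maximum of 20 × 3 = 60, so this exclusion can still be met.
- Contraindication to varenicline (Section 6).
- Serious or untreated psychiatric illness (Sections 6 and 9b).
- Severe past or present psychiatric symptoms, or suicidal behaviours (Section 9b).
- Being judged at high risk of problems on varenicline (Section 9b).
- Medical clearance, which must confirm that no exclusion is violated (Section 5a, Medical Assessment). The inputs it names are laboratory results, the medical survey and vital signs. The text does not say that list is complete.
- Study team discretion (Section 6).

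None of these says what to do when the suicidality screens are blank. Discretion could be used, but using it only because the screens are blank would conflict with the Section 9b statement on declining.

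**Step 6. Which decline statements conflict with requiring the screens.** Only the opening paragraph of Section 9b speaks of eligibility. The other two statements permit declining and are silent on its consequence, so they are compatible with an entry requirement.

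**The case against.** The strongest reply on the threshold is that it corrects itself. A rule that rejects every applicant cannot be followed, so staff would notice at once and use the working rule in Section 5a. No endpoint or analysis changes and no one at risk is let in. All of that stands, and it is why the point is minor. It does not remove the need to correct a wrong threshold in the operative eligibility list.

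A reader might infer that the wrong threshold reaches much further. Section 5f says "Participants failing to continue to meet any of the inclusion/exclusion criteria will be removed from the study", the BDI entry says "The BDI will be administered at every study visit to assess ongoing changes to mood", and under Section 5b participants "will return to the clinic on approximately a weekly basis during study weeks 1-12". That would give 1 screening + 12 weekly visits = 13 administrations per participant governed by the faulty rule. The documents do not support this. Read so literally, the removal rule would also discharge every successful quitter, because Section 6 requires a cotinine-positive urine sample, and everyone after surgery, because it requires an operation scheduled 5 to 10 weeks ahead. The examples in Section 5f are new clinical problems, and on-study answers to item 9 have their own rule in Section 9b. The threshold governs the screening BDI.

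On declining, the reply is that the clause is a general protection against discomfort, that it does not promise enrolment, that Section 9b itself says participants will be screened by questionnaire, and that medical clearance covers all exclusions. This is fair and shrinks the gap. It does not supply a rule for a blank screen.

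**Conclusion.** Section 6 is wrong as written: ≥ 0 on the BDI suicide item should be > 0. The discrepancy is one score value out of four, at the screening assessment, and it errs towards excluding people. The finding assumes that the printed symbol is in the source; the 0 to 3 range assumes equally scored items.

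The missing exception in Section 9b is a lesser matter, worth a clarification. It has no calculable size, because the documents give no rate of declining and none is assumed here.

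Two stronger readings should be resisted. One is that the trial cannot enrol anybody, so that none of the 40 planned screenees who answered the item could qualify. That follows from Section 6 alone, but Section 5a supplies a usable rule that staff would probably apply. The other is that an applicant with suicidal thoughts can enter unchecked simply by skipping the forms. The text says only that declining is not itself a ground for ineligibility; the safeguards listed above still apply, and mood is reassessed at each visit. Overall severity is minor.

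**What to change.** 1. In Section 6, change ≥ 0 to > 0 for the BDI suicide question, and name it as item 9 at screening so that it matches Section 5a.
2. In the opening paragraph of Section 9b, add one sentence: a completed BDI item 9 and C-SSRS at screening are required for enrolment; applicants may still decline either, but are told that they then cannot be enrolled; the right to decline is otherwise unchanged. Section 9a and the later questionnaire paragraph of Section 9b need no edit.

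The cost is a wording amendment to two places. No procedure is added, because Section 5a already gives the BDI at screening and the C-SSRS at baseline. The downside is that an occasional applicant who declines these screens is lost to the study.

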5. Study Procedures

- a. Study design, including the sequence and timing of study procedures (distinguish research procedures from those that are part of routine care).

In this two-year open-label feasibility study, 20 smokers who are planning to undergo elective surgery will complete a 12-week intensive pre- post-surgical smoking cessation intervention, involving three major components: (1) varenicline administration, (2) standardized smoking cessation counseling, and, during the pre-surgery phase, (3) incentives for urine samples that test negative for cotinine. Upon verifying that all study eligibility criteria are met, patients will enter the intervention phase of this study. During this phase, patients will attend weekly study visits to receive the pre-surgical component of the intensive smoking cessation intervention in approximately the 4-6 weeks leading up to surgery, and complete approximately six additional weekly study visits post-surgery in order to continue with the post-surgical varenicline administration component of the intensive smoking intervention for a total of 12 weeks, and to allow for in-person assessment of post-surgical smoking cessation and surgical recovery outcomes. Finally, participants will be scheduled for an in-person follow-up visit approximately one month following completion of the study to assess study outcomes. In some cases, this follow-up period may extend as long as six months to collect data that ensures study outcomes are being met.

Recruitment: We will recruit participants via physician or self-referrals. A number of strategies may be utilized to identify potential participants early in the elective surgical process. We will provide medical departments and physicians detailed information about study eligibility criteria and procedures and encourage them to provide potentially eligible patients with information to contact the study team. We will also post flyer advertising a smoking cessation study for elective surgical patients in common areas and waiting rooms to enable potential participants to contact us directly. All interested individuals will be instructed to call the study team and complete a brief phone screen to establish initial study eligibility before conducting a full screening visit.

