Screening: We are proposing to screen 40 individuals and complete 20 people for this initial study, which is consistent with other pilot/feasibility studies and will provide enough data to indicate whether a signal exists that would support further evaluation of this treatment approach in a larger-scale clinical trial study.

All participants will read and sign the informed consent with a trained staff member before conducting the screening visit, which will include self-report of smoking and other related variables, urinalysis verification of recent smoking, illicit drug, and pregnancy status, a medical history to determine medical eligibility, and completion of baseline decision-making measures. Participants will also provide written permission for study staff to access medical records to verify postsurgical outcomes and analgesic use, for study outcome measures.

Screening and Study-related Measures:

The following measures will be utilized during the study to determine eligibility and provide data necessary to complete the study aims. Individuals enrolled into the study will complete assessments weekly during treatment with one follow-up assessment 30 days after study completion. These data will be used to monitor changes in smoking status, mood or behavior changes related to medication or tobacco abstinence, health and pain-related outcomes, and vital signs.

- Time-Line Follow-Back (TLFB; Sobell et al., 1988): a validated self-report measure to record daily behaviors, including medication compliance and use of tobacco, alcohol, and other drugs/medications.

A past 30-day assessment will be conducted at baseline, with weekly assessments during the study

- Smoking History: brief self-report questionnaire of smoking history, quit attempts, use of pharmacotherapy, interest in quitting smoking, perceived ability to quit smoking and perceived health risk of smoking.
- Fagerström Test for Nicotine Dependence (FTND; Heatherton et al., 1991): 6-item self-report measure of nicotine dependence.
- Contemplation Ladder (Biener & Abrams, 1991): graphical description of process of change in relation to the need to quit smoking. Score ranges from 0 (no thoughts of quitting) to 10 (taking action to quit).
- Minnesota Nicotine Withdrawal Questionnaire-Revised (MNWQ-R; Hughes & Hatsukami, 1986): The 15- item self-report measure of nicotine withdrawal with good reliability and validity.

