unwilling/unable to adhere to the study schedule, be unwilling to provide study access to medical records, having a serious and/or untreated medical and/or psychiatric illness that may jeopardize study participation, or being otherwise judged by the study team to be inappropriate for study participation.

7. Drugs/ Substances/ Devices

- a. The rationale for choosing the drug and dose or for choosing the device to be used.

We have selected varenicline for this study because it is a gold-standard pharmacotherapy for smoking cessation, it produces the highest levels of smoking cessation of all FDA-approved medications, and because it has fewer medication interactions relative to the other common smoking-cessation pharmacotherapy bupropion. This will minimize the likelihood that participants will be required to end varenicline administration following surgery due to a new prescription related to their surgery. There is nothing experimental about the use of varenicline in this study.

Varenicline will be administered as clinically indicated for a 12-week period and will begin approximately 4-6 weeks prior to surgery. All participants will undergo the standard 1-week dose induction period (0.5mg QD Days 1-3, 0.5mg BID Days 4-7) before transitioning to a full maintenance dose (1mg BID). The target-quit date (TQD) will be on Day 8 (week 2) and will coincide with the 1st day of the maintenance dose, consistent with recommended guidelines. Varenicline will be packaged into blister packs by our research pharmacy. Participants will receive a 1-week supply of varenicline (with 3 days of extra doses in the event of an unpredicted event) in blister packs at each study visit (except at the study visit immediately prior to the participants' scheduled surgery, at which time they will receive a 2-week supply with 3 days of extra doses). Dispensing medication at weekly intervals (vs. monthly prescriptions) is a standard approach in our research unit that allows us to more closely track medication adherence and adverse events, and will help encourage participants to attend weekly visits for primary data collection purposes.

Varenicline adherence will be assessed using a weekly medication adherence self-report questionnaire. We will also save an aliquot of urine from each weekly visit that will be tested for evidence of varenicline by a commercial laboratory. Percent medication adherence rate may be used as a covariate in the study analyses.

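### Section 6 sets the BDI suicide-item exclusion at ≥ 0, which every answer meets; it should read >0 at screening, as in section 5.a

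*Combined protocol and SAP*

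**What the plan says.** Section 6 (Inclusion/Exclusion Criteria) excludes people with "a score ≥ 0 on the suicide question of the BDI". The BDI entry in section 5.a, under the screening and study-related measures, says that participants "who endorse >0 on the suicidal thoughts question (item 9) during screening will be excluded". The two differ in the symbol, and only section 5.a gives the item number and the time point.

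The eligibility criteria are used at three points:

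- Entry, section 5.a: "Upon verifying that all study eligibility criteria are met, patients will enter the intervention phase of this study".
- Medical clearance, the Medical Assessment entry in section 5.a: staff confirm that no exclusion is breached before clearing a participant.
- Removal, section 5.f: "Participants failing to continue to meet any of the inclusion/exclusion criteria will be removed from the study".

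Section 9.b deals separately with suicidal thoughts reported during the study. Any endorsement on the BDI leads to the C-SSRS, and mood changes in the weekly update lead to assessment by a qualified investigator.

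Section 9.a also states two firm exclusions that section 6 does not name. One is taking bupropion. The other is, for women, planning a pregnancy or declining adequate contraception during the study. The nearest wording in section 6 is "Exclusion criteria will include being contraindicated for varenicline use", plus current pregnancy or breastfeeding.

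**The concern.** An exclusion that every respondent meets cannot screen anyone. Staff have to disregard the printed criterion and use section 5.a instead. This line is part of the suicide-safety screen for a drug whose neuropsychiatric effects the protocol treats as its most worrying risk, and section 9.b relies on the exclusion criteria to keep risk minimal.

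The missing time point is a second problem. The BDI is given at every visit. If only the symbol were corrected, a participant who endorsed item 9 in a later week would meet a section 6 exclusion, and 5.f would call for removal. Section 9.b instead calls for the C-SSRS and clinical assessment.

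The bupropion and contraception rules are a lesser matter of placement. They bind already, but someone working from section 6 alone would not see them.

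**Working it through.** **Inputs.** From the BDI entry in section 5.a: 21 items; total score bands running from 0 to 63. From Screening in section 5.a: "We are proposing to screen 40 individuals and complete 20 people for this initial study".

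**Step 1: item range.** A total of 0 is possible, so with non-negative item scores the lowest score on every item is 0. If items are scored equally, the highest is 63 / 21 = 3. The suicide item then takes the values 0, 1, 2 and 3.

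**Step 2: apply each rule.**

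| Rule | Scores excluded | Scores eligible |
|---|---|---|
| Section 6: ≥ 0 | 0, 1, 2, 3 (4 of 4) | none |
| Section 5.a: >0 | 1, 2, 3 (3 of 4) | 0 |

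The rules differ only at a score of 0, which is the score for no suicidal thoughts. The section 6 result needs only the minimum of 0, not the equal-scoring assumption.

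**Step 3: literal consequence.** Under ≥ 0, all 40 planned screens are excluded: 40 − 40 = 0 eligible, against 20 completers wanted. Under >0, anyone scoring 0 remains eligible on this criterion.

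**Step 4: timing.** Take a participant who scores 0 at screening and 1 at a later visit.

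- Section 6 with >0 and no time point, read with 5.f: remove.
- Section 9.b: administer the C-SSRS and assess.
- Section 6 with >0 at screening: the entry criterion is still met, so section 9.b governs. Section 5.f still separately withdraws anyone who develops suicidality requiring treatment.

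**Step 5: section 9.a exclusions against section 6.**

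| Exclusion stated in section 9.a | Named in section 6? |
|---|---|
| Taking bupropion | No; at most implied by the general varenicline contraindication clause |
| Planning pregnancy or refusing adequate birth control | No; only current pregnancy or breastfeeding |

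The plan states no figure on this point to reproduce.

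**The case against.** The strongest reply is that ≥ 0 is an obvious slip. Section 5.a gives the correct rule with item number and timing, no site would turn away everyone, and the error runs toward excluding people rather than exposing them to risk. That stands as to consequence, and it is why the point is minor. It does not make the printed threshold right.

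It can also be said that 5.f is not meant to re-test every entry criterion. Section 6 requires a cotinine-positive sample, and applying that throughout would remove every successful abstainer. This is a fair reading of intent. It is also a good reason to write the time point into the suicide-item criterion, so that nobody has to infer it.

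On bupropion and contraception, section 6 introduces its list with wording that is not exhaustive, it ends with a study-team judgement clause, and the section 9.a sentences are mandatory in their own right. This stands. A reader might infer that people taking bupropion, or women refusing contraception, would be enrolled. The documents do not support that; the gap is in where the rules are printed.

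A reader might also infer a contradiction between "past year suicidal ideations or behavior on the C-SSRS" in section 6 and section 9.b, which excludes severe psychiatric symptoms, including suicidal behaviour and psychosis, whether past or present. The documents do not support this either. The first rule covers any ideation or behaviour in the past year; the second covers severe symptoms with no time limit. They add to each other, and section 6 also has a general clause for "having a serious and/or untreated medical and/or psychiatric illness that may jeopardize study participation". Restricting section 9.b to the past year would admit people it now excludes.

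**Conclusion.** Wrong as written, and minor. The section 6 threshold is met by 4 of 4 possible answers where section 5.a intends 3 of 4, so read literally it leaves 0 of 40 screens eligible. That result rests on an item minimum of 0, which follows from the BDI range in the document. The intended rule is clear from section 5.a, so the practical risk is confusion at screening and at removal. A reader might take the figure of 0 of 40 as a forecast that recruitment will fail. It is only the literal consequence of the text, and nothing suggests that staff would apply it.

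The two section 9.a exclusions are accurate but secondary: listing them in section 6 restates rules that already bind. The documents give no rates for bupropion use or refusal of contraception, so no count of people affected is offered. No endpoint, analysis or sample size is touched.

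**What to change.** In section 6, replace the suicide-item criterion with: *a score >0 on the BDI suicide item (item 9) at screening*.

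In the same amendment, add two items to the section 6 exclusions for consistency with section 9.a: *current bupropion use*, and *planning pregnancy or refusing adequate birth control during the study*.

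Leave the section 9.b exclusion of severe suicidal behaviour and psychosis as it is, with no time limit, alongside the past-year C-SSRS rule.

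The cost is a short text amendment to one section. It needs no new procedure, data item or analysis, and the intended population does not change, because each edit restates a rule already in section 5.a or 9.a.
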